(✓) Undergrad./post grad. (indicate resident, fellow, master, PhD student)

5. Keywords:

High-Frequency Ventilation, Intermittent Positive-Pressure Ventilation, Newborn, Noninvasive Ventilation

6. Background and rationale

Non-invasive ventilation (NIV) in neonate has 4 main modes

1. Nasal continuous positive airway pressure (nCPAP)
2. Nasal biphasic CPAP (nBi-CPAP)
3. Nasal intermittent positive pressure ventilation (nIPPV) or nasal synchronized IPPV (nSIPPV)
4. Nasal high frequency oscillation (nHFO)

From meta-analyses, respiratory and extubation failure in n(S)IPPV and nHFO modes were lower than nCPAP. However, most studies were enrolled by primary support but few studies from post-extubation and high-heterogeneity.

Knowledge gap

The comparison of n(S)IPPV and nHFO is still limited in neonatal period. In ClinicalTrial.gov, there are 3 registry studies in Table 1.

Table 1 The studies were registered in ClinicalTrial.gov

U.S. National Library of Medicine		Find Studies	About Studies	Submit Studies	Resources	About Site
ClinicalTrials.gov						
Home > Saved Studies		Saved Studies (3)				
Saved Studies						
Row	Saved	Status	Study Title	Conditions	Interventions	Locations
1		Recruiting	Nasal High-frequency Jet Ventilation (nHFJV) Following Extubation in Preterm Infants	
 • Infant, Premature • Respiratory Failure • Respiratory Insufficiency • Respiratory Distress Syndrome in Premature Infant 	
 • Other: Nasal high-frequency jet ventilation (nHFJV) • Other: Nasal intermittent positive pressure ventilation (NIPPV) 	
 • University of Utah, Salt Lake City, Utah, United States • Primary Children's Hospital, Salt Lake City, Utah, United States
2		Recruiting	A Trial Comparing Noninvasive Ventilation Strategies in Preterm Infants Following Extubation	
 • Intubated Infants Were Intend to Extubation Using Noninvasive Ventilation Strategies 	
 • Device: NHFV • Device: NCPAP • Device: NIPPV 	
 • Daping Hospital and the Research Institute of Surgery of the Third Military Medical University, Chongqing, Chongqing, China
3		Unknown [†]	Nasal High Frequency Oscillatory Versus Nasal Intermittent Positive Pressure Ventilation in Neonate After Extubation	
 • Respiratory Insufficiency 	
 • Device: NIPPV • Device: NHFOV 	

[†] Study has passed its completion date and status has not been verified in more than two years.

Activate Windows [^ TO TOP](#)
Go to Settings to activate Windows.

[figure not shown]
[For Patients and Families](#) | [For Researchers](#) | [For Study Record Managers](#)

7. Objective(s) of the study

Primary objective: To assess the pCO₂ after 2 hours of nHFO compared with 2 hours of nSIPPV in crossover study.

Secondary objective: To assess the reintubation rate within 7 days between non-invasive ventilations (nHFO vs nSIPPV) from the latter NIV mode in parallel study

8. Study flow diagram and/or Conceptual framework

9. Literature review

Mechanical ventilation was introduced to treat respiratory failure in preterm infants or sick neonates then improvements in survival.^{1,2} However, the complications from short or long term use of ventilation can result in unintended harm or burden (e.g., air leak syndrome, pneumonia, bronchopulmonary dysplasia, neurological injury, retinopathy of prematurity).^{3,4} To reduce these risks, clinicians should aggressive extubated neonates as early as possible. Respiratory (focus on blood gas as well as partial pressure CO₂ [pCO₂]) or extubation (focus on clinical condition as well as reintubation) failure was worrisome in pediatrician and parents if the neonate was reintubated owing to complete recovery of lung disease or inadequate respiratory drive.

[figure not shown]
[figure not shown]
[figure not shown]
Non-invasive ventilation (NIV) was supported for primary respiratory support (initial mode before endotracheal intubation) or post-extubation. Nasal continuous positive airway pressure (nCPAP) was familiar to NIV mode in neonatal respiratory support. Nowadays, the new NIV modalities are nasal intermittent synchronized positive pressure ventilation (nSIPPV) and nasal high frequency oscillation (nHFO).

[figure not shown]
[figure not shown]
[figure not shown]
To increase the likelihood of nCPAP success, other new modalities of NIV may be interesting. From theory, nSIPPV and nHFO combines peak inspiratory pressure (PIP) with synchrony and high-frequency oscillations without synchrony above CPAP, respectively. From meta-analysis, nSIPPV and nHFO were statistically significant superior than nCPAP both respiratory and extubation failure in neonate (**Table 2, Fig. 2-5**).^{5,6}

The aim of our study was to investigate the efficacy of nHFOV and nSIPPV for CO₂ clearance and reintubation rate after extubated neonates. We hypothesized that nHFOV mode would improve CO₂ clearance better than nSIPPV mode.

Table 2 Meta-analyses compared nIPPV, nSIPPV, nBi-CPAP, and nHFO to nCPAP

Intervention	Control		Respiratory failure	Reintubation within 7 days
Interventions to improve rates of successful extubation in preterm infants: a systematic review and meta-analysis. JAMA Pediatr 2017;171:165-74.				
n(S)IPPV or nBi-CPAP	nCPAP	RR (95%CI)	.70 (.60, .81)	.74 (.64, .85)
• 9 RCTs (Fig. 1-2)		RD (95%CI)	-.13 (-.18, -.08)	-.10 (-.15, -.05)
		NNT (95%CI)	8 (5-13)	10 (6-20)
		I ²	66%	51%
nSIPPV	nCPAP	RR (95%CI)	.25 (.15, .41)	
• 5 RCTs (Fig. 1)		RD (95%CI)	-.33 (-.43, -.23)	
		NNT (95%CI)	4 (2-5)	
		I ²	0%	
Noninvasive high-frequency oscillatory ventilation as respiratory support in preterm infants: a meta-analysis of randomized controlled trials. Respir Res 2019;20:58.				
nHFO	nBi-CPAP or nCPAP			
• 5 RCTs (1 postextubation, 4 primary support)		pCO ₂ , WMD 95%CI), I ²	-4.61 (-7.94, -1.28), 67%	
		ΔpCO ₂ , WMD 95%CI), I ²	-4.89 (-8.36, -1.42), 70%	
• 7 RCTs (1 postextubation, 6 primary support)		RR (95%CI), I ²		.50 (.36, .70), 0%

eFigure 1. NIPPV vs. CPAP: Respiratory failure; subgroup analysis by method of NIPPV**Fig. 2 Respiratory failure compared nSIPPV, nIPPV, mixed modes to nCPAP****A Respiratory failure****B Reintubation****Fig. 3 Respiratory failure and reintubation compared n(S)IPPV to nCPAP**

pCO₂ levelsΔpCO₂**Fig. 4** pCO₂ and ΔpCO₂ between nHFO and nBi-CPAP or nCPAP**Fig. 5** Intubation between nHFO and nBi-CPAP or nCPAP

10. Research methodology

10.1. Study design: Non-blinded prospective (pragmatic) randomized controlled cross-over study

10.2. Setting of the study/Trial site: Neonatal Intensive Care Unit (NICU), Songklanagarind Hospital

10.3. Target population: NICU admitted neonate

10.4. Study population: Ventilated neonate

10.5. Inclusion criteria

1. Born in hospital and admit in NICU
2. The first endotracheal intubation and need NIV if extubation
3. Neonate has not been intervened from another RCT study

10.6. Exclusion criteria

1. Major congenital anomalies or chromosomal abnormalities
2. Neuromuscular diseases
3. Upper respiratory tract abnormalities
4. Suspected congenital lung diseases or pulmonary hypoplasia
5. Need for surgery known before the first extubation
6. Grade IV intraventricular hemorrhage (IVH) occurring before the first extubation
7. Palliative care
8. Unplanned extubation
9. Parents' decision not to participate

10.7. Participant withdrawal criteria

1. Parents' decision not to participate
2. Reintubation during 4-hour cross-over study

10.8. Study termination criteria

Interim analysis every 6 months, study will stop when

- Reintubation rate in nHFO more than 30% (2 time of 15% in Fig. 4)
- Reintubation rate in nSIPPV more than 60% (2 time of 29% in Fig. 2)
- Reintubation rate between nHFO and nSIPPV difference more than 30%

10.9. Sample size calculation

RCT for continuous data	
Formula[ref]:	
$n_{trt} = \frac{(z_{1-\frac{\alpha}{2}} + z_{1-\beta})^2 \left[\sigma_{trt}^2 + \frac{\sigma_{con}^2}{r} \right]}{\Delta^2}$	
$r = \frac{n_{con}}{n_{trt}}, \Delta = \mu_{trt} - \mu_{con}$	
Mean in treatment group (... 35.1	
Mean in control group (μco... 43	
SD. in treatment group (σt... 7.5	
SD. in control group (σcon) = 6	
Ratio (r) = 1	
Apha (α) =	0.01 0.05
Beta (β) =	0.1 0.2
Calculate Clear	
Sample size: Treatments = 12, Controls = 12	
RCT for binary data	
Formula (without continuity correction)[ref]:	
$n_{trt} = \left[\frac{z_{1-\frac{\alpha}{2}} \sqrt{p_1 \bar{q}_1 (1+\frac{1}{r})} + z_{1-\beta} \sqrt{p_1 q_1 + \frac{p_2 q_2}{r}}}{\Delta} \right]^2$	
$p_1 = P(\text{outcome treatment}), q_1 = 1 - p_1$	
$p_2 = P(\text{outcome control}), q_2 = 1 - p_2$	
$\bar{p} = \frac{p_1 + p_2 r}{1+r}, \bar{q} = 1 - \bar{p}, r = \frac{n_{con}}{n_{trt}}$	
P(outcome treatment) = .10	
P(outcome control) = .17	
Ratio (r) = 1	
Alpha (...	0.01 0.05
Beta (β) =	0.1 0.2
Calculate Clear	
Sample size: Treatments = 373, Controls = 373	
Sample size by using a continuity correction: Treatments = 401, Controls = 401	

10.10. Study procedure(s)/stage(s)

[figure not shown]
This study was blocked and stratified randomization. Subjects were equally (1:1) randomized to one of the two treatment sequences (nHFOV–nSIPPV, nSIPPV–nHFOV). The allocation sequence was computer generated by box of four. The allocation concealment was ensured by using identical, opaque, sealed envelopes. An envelope was drawn by a dedicated nurse immediately after enrolment of the infant. The participants were stratified by gestational age and oxygen index (OI = mean airway pressure [MAP]*FiO₂*100/PaO₂). The participants were on the non-blinded and randomized NIV mode for 2 hours and blood gas was analyzed then switched to another NIV mode for 2 hours (cross-over) and blood gas was analyzed repeatedly. There was not a washout period between 2 NIV modes then the last NIV mode was on until no need NIV. We will register in ClinicalTrials.gov before start and enrollment of the participants.

Extubation criteria: The ventilated neonate had a targeted oxygen saturation (SpO₂ > 90%) during on FiO₂ < 0.4 and acceptable blood gas (pH > 7.25, PaCO₂ < 60) with the respiratory setting of

[figure not shown]
1. HFO: flow 6-10 L/min, frequency 10 Hz, MAP = “6-7 (preterm), 7-9 (term)” cmH₂O, dP = 12-20, I:E = 1:1
2. AC: flow 6-10 L/min, rate 30/minute, PIP 12-15 cmH₂O, PEEP = 3 cmH₂O

Intervention nHFOV and nSIPPV were generated by neonatal ventilators (SLE6000 infant ventilators, United Kingdom) using bi-nasal prongs (RAM cannula, NEOTECH[®], USA) or the nasal mask of the same type for both ventilation modes. The size of the prongs was determined by the infant's weight. The largest possible prongs were used, with a snug fit to avoid leakage. Pacifier for preterm and term neonate (JollypopTM, USA) was taken to avoid leakage from the mouth. The disposable ventilator circuit (Fisher & Paykel RT268TM, Evaqua Dual Limb Infant Breathing Circuit Kit with Evaqua 2 Technology and Pressure Line, Flow > 4L/min, New Zealand) was used. The initial NIV setting was⁷

1. nHFO: flow 8-10 L/minute, frequency 10 Hz, MAP = "MAP (before extubation) + 2" or "8 (preterm), 10 (term)" cmH₂O, dP = "2-3 times of MAP with visible chest oscillations" or 25-35 cmH₂O, I:E = 1:1, FiO₂ = "FiO₂ (before extubation) + 0.1-0.2" keep targeted SpO₂ 90-94%

2. nSIPPV: flow 8-10 L/minute, rate 60/minute, PIP = "PIP (before extubation) + 2-5" or "20 (preterm), 25 (term)" cmH₂O, PEEP = 5 cmH₂O, IT = 0.5 s, FiO₂ = "FiO₂ (before extubation) + 0.1-0.2" keep targeted SpO₂ 90-94%. The highest trigger sensitivity avoiding auto triggering was selected.

The monitoring after extubation was vital signs, clinical manifestations, respiratory distress, and umbilical arterial blood gas. The first blood gas before extubation was routine obtained. After randomization, the initial NIV was started then blood gas was obtained after 2 hours. The participant was switched to another NIV and blood gas was obtained after 2 hours. The participant was continued with the last NIV mode until the NIV was stopped. The participant was excluded if severe respiratory failure with reintubation during 4 hours after intervention. The parameters were adjusted or titrated according to patient tolerance and disappeared respiratory distress, the intervention went on until 4 hours. The NIV was stopped to "room air, oxygen box, low or high flow cannula" when

1. nHFO: MAP = 5-6 cmH₂O, dP = 10-15
2. nSIPPV: PIP/PEEP = 10-12/3-5 cmH₂O

Criteria for extubation failure or reintubation were as follows:

1. Cardiorespiratory arrest or any type of pulmonary hemorrhage
2. Persistent low blood pressure without response to volume expander and vasoactive agents
3. Stupor or persistent drowsiness after initial correction and care
4. Severe respiratory distress
5. Two hours of respiratory acidosis with PaCO₂ > 70 mmHg and pH < 7.2
6. Two hours of hypoxia with PO₂ < 50 mmHg with FiO₂ > 0.6, and maximal pressures given (MAP 20 and PIP 25 cmH₂O in the nHFOV and nSIPPV group, respectively)
7. Apnea occurring three or more times per hour and a heart rate less than 100/min or apnea with required bag-and-mask ventilation.
8. Severe post extubation stridor

In case of extubation failure, the study period was ended prematurely for the respective infant, pCO₂ was measured by blood gas analysis and a mode of ventilation was chosen as

deemed appropriate by the attending staff. In general, infants were treated with intravenous aminophylline then oral caffeine base and were supported before and after the study.

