11.1. Possible risks/effects in the study, including preventive and alleviation measures

Both interventions, the participants were obtained the blood samples before and after intervention via arterial line to minimize pain from phlebotomy.

The volume of blood sample was 0.4 mL including before and after tests. The maximum allowable blood draw volumes were shown in **Figure 6**.

Maximum allowable blood draw volumes:

PATIENT'S WEIGHT		TOTAL VOLUME	MAXIMUM mL IN ONE BLOOD DRAW	MAXIMUM mL IN A 30-DAY PERIOD
Kg	lbs	mL		
1	2.2	100	2.5	5
2	4.4	200	5	10
3	3.3	240	6	12
4	8.8	320	8	16
5	11	400	10	20

Figure 6 Maximum allowable blood draw volumes

11.2. Describe the process/system for assuring confidentiality and the privacy of the research participants/communities

The record form was unidentifiable enrolled patients; therefore, name or hospital number would not be filled in the record form. The data would be kept in secret files and only principal investigators and recorders could access to these data during recruitment of the participants, during data collection, during transcription, and data analysis, and dissemination of research results.

11.3. Benefits of the study for participants and the community/country including how findings of the study use for strengthening community.

The result of this study may be the choice of post-extubation via nSIPPV and nHFO (head to head comparison)

11.4. Informed consent process: Process/method of invitation the participants to participate in the research, such as personal contact, referral from other(s), brochure, and announcement, etc.

The parents of intubated neonates without exclusion criteria would be pursued to enrolled in this study by the dedicated nurse. The parents would receive informative documents with explaining the entire data about 30 to 60 minutes or until the parent were crystal clear about the study detail by the nurse. If the parents allowed the patients to enroll in the study, they would sign the signature in the informed consent's document.

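### A fixed, published block size of four in an open-label single-unit trial lets up to one third of allocations be worked out in advance, which mainly exposes the reintubation comparison

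*Combined protocol and SAP*

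**What the plan says.** Section 10.10 describes the allocation: "This study was blocked and stratified randomization", in a 1:1 ratio to the two sequences, and "The allocation sequence was computer generated by box of four". No other block size is mentioned. On strata it says "The participants were stratified by gestational age and oxygen index", and the text gives neither cut-points nor the number of strata.

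On concealment, 10.10 says "The allocation concealment was ensured by using identical, opaque, sealed envelopes" and "An envelope was drawn by a dedicated nurse immediately after enrolment of the infant". Section 11.4, on consent, says that parents of eligible infants "would be pursued to enrolled in this study by the dedicated nurse", and the nurse also explains the study to them.

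Section 10.1 calls the trial a "Non-blinded prospective (pragmatic) randomized controlled cross-over study", and 10.2 names one NICU. Under section 7, the secondary objective compares reintubation within 7 days between the infants' latter modes. Under 10.10, the second mode continues until NIV is no longer needed, so the randomised sequence fixes the arm for that comparison.

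The text does not mention varied block sizes, withholding the block size from recruiters, numbered envelopes, a separate envelope holder or central release.

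**The concern.** A sealed opaque envelope hides the card inside it. It does not hide what the earlier cards in the same block imply. With blocks of four and two sequences, each block holds two of each. Once two infants in a block have had the same sequence, the rest of the block is known; otherwise the fourth is known after three. Treatment is open and all infants are in one unit, so past allocations are visible to staff.

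Drawing the envelope after enrolment does not close this gap, because the deduction can be made before parents are approached. There is room to act on it: inclusion criterion 2 in 10.5 turns on a judgement that the infant will need NIV, and the timing of the approach to parents is not fixed.

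What is at stake is mainly the reintubation comparison, which is between infants. The stopping rules in 10.8 also use reintubation rates by mode. The pCO2 contrast is less exposed. The treatment-effect test in 10.14 compares sequences, but it does so on within-infant differences, so a stable difference in severity between the sequence groups largely cancels.

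**Working it through.** **Inputs.** Block of four, 1:1, stratified (10.10). Reintubation 0.10 and 0.17; pCO2 means 35.1 and 43, SDs 7.5 and 6 (10.9). Significance level 0.05 (10.14). The beta selected is not visible in the text; 0.2 is inferred because it reproduces the stated sizes. The number of strata is not given; 4 to 9 equal strata are assumed.

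**The plan's own sizes.**
- pCO2: (1.960 + 0.842)² × (7.5² + 6²) / 7.9² = 11.60, so 12 per group, or 24 in all.
- Reintubation: the 10.9 binary formula gives 372.9, so 373 per group; with continuity correction 401.0, so 401 per group. Totals are 746 and 802.

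All three match 10.9. The plan does not say which target governs enrolment, so both ends are carried forward.

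**Allocations known with certainty, complete blocks of four.** There are six balanced orders. Two (AABB, BBAA) fix the last two places; the other four fix only the last. The share is (2 × 2 + 4 × 1) / (6 × 4) = 8/24 = 33.3%. By position the probabilities are 0, 0, 1/3 and 1.

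**Best-guess accuracy.** By position: 1/2, 2/3, 2/3 and 1. The mean is 17/24 = 70.8%, against 50% with no information.

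**Incomplete blocks.** A stratum with c infants has an expected floor(c/4) × 4/3 certain allocations, plus 1/3 if three infants are left over. Taking c as binomial with N infants over S equal strata:

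| Infants | Strata (assumed) | Certain allocations | Share |
|---|---|---|---|
| 24 | 4 | 6.3 | 26% |
| 24 | 6 | 5.5 | 23% |
| 24 | 9 | 4.1 | 17% |
| 746 | 4 | 247 | 33% |
| 746 | 9 | 245 | 33% |

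**Other schemes.** Fixed blocks of 6 give 25% and fixed blocks of 8 give 20%, by the same enumeration. For sizes drawn at random from 4, 6 and 8, simulation with an observer who knows the set of sizes but not each block's size gives about 2.3% certain and 68% best-guess accuracy.

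**Bias, for illustration only.** Bias in the risk difference = share certain × fraction of those steered × risk gap between the infants steered to each arm. With 1/3 certain, 25% to 100% steered and a gap of 5 to 10 points (both assumed), this runs from 1/3 × 0.25 × 5 = 0.4 points to 1/3 × 1 × 10 = 3.3 points. The design difference is 17 − 10 = 7 points.

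**The case against.** The strongest reply is that this is a weaker choice and not an invalid method. Fixed blocks with opaque sealed envelopes opened after enrolment are a recognised arrangement, and the primary objective is largely protected. To exploit the blocks, someone must know the size and keep a separate tally for each stratum. One stratum factor, the oxygen index, depends on airway pressure, FiO2 and PaO2, which change over time, and the plan does not say when it is fixed. Extubation has numerical criteria, and every infant who completes four hours receives both modes, which weakens any motive to steer. All of this lowers the risk. It does not remove it, because the latter mode continues and defines the reintubation arm.

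A reader might infer three stronger things that the documents do not support.

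- **That one third applies whatever the enrolment.** It is the figure for complete blocks, and falls to about 17% to 26% if only 24 infants are spread over several strata.
- **That one person recruits and draws.** Section 10.10 refers to a dedicated nurse and 11.4 to the dedicated nurse. That is a shared role, not proof of one individual.
- **That varying the block size is enough.** It removes nearly all certainty but leaves guessing well above chance.

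**Conclusion.** The weakness is real and cheap to remove. As written, up to one third of allocations could be known in advance: about 33% at 746 infants, and about 17% to 26% at 24 infants under the assumption of 4 to 9 equal strata. These are shares of allocations that could be deduced by someone who knows the block size and tracks past allocations within strata. The documents do not show that anyone would do so.

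The exposure lies mainly in a secondary outcome, 7-day reintubation by latter mode, and in the 10.8 stopping rules that use reintubation rates. A reader might go further and conclude that the reintubation result will be biased, or biased by 0.4 to 3.3 points. The documents do not support that: the range rests wholly on assumed steering rates and risk gaps. The case for change is that selection bias cannot be reliably removed at analysis, while preventing it at the design stage costs little.

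**What to change.** In 10.10:

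1. Replace the fixed block of four with permuted blocks of randomly varying size within strata, for example 4, 6 and 8. State in the protocol only that sizes vary. Keep the sizes in a restricted document that recruiting staff cannot see.
2. Have existing staff who do not recruit hold sequentially numbered envelopes for each stratum and release the next one only after consent and the infant's stratum have been recorded. This is needed because the first step alone lowers best-guess accuracy only from about 71% to 68%.
3. Make 11.4 consistent, so that whoever approaches parents does not hold or open envelopes.

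The cost is one line in the randomisation program, a few sentences of text, and an arrangement for a non-recruiting member of staff to be reachable at extubation.

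The statistical price is a slightly larger possible imbalance between sequences. In simulation with 24 infants, the chance of an overall imbalance of 6 or more rises from under 1% to about 2% with 4 strata, and from about 7% to about 14% with 9 (strata numbers assumed). Larger blocks leave more of them incomplete, so this matters most if only about 24 infants are enrolled.

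### Randomisation is tied to enrolment, not to planned extubation, so three exclusion criteria can still be met after open-label allocation, and the plan does not say how such infants are handled

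*Combined protocol and SAP*

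**What the plan says.** Recruitment (section 11.4): "The parents of intubated neonates without exclusion criteria would be pursued to enrolled in this study by the dedicated nurse". Enrolment is then described as parental agreement and signature: "If the parents allowed the patients to enroll in the study, they would sign the signature in the informed consent's document".

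Randomisation (section 10.10): "An envelope was drawn by a dedicated nurse immediately after enrolment of the infant". The envelopes are opaque and sealed, allocation is stratified by gestational age and oxygen index, and the trial is not blinded (sections 10.1 and 10.10). The same section says that a routine blood gas is taken before extubation and that the first NIV mode starts after randomisation. It gives no interval between envelope and extubation.

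Eligibility: inclusion criterion 2 (section 10.5) looks ahead to an extubation that has not yet happened: "The first endotracheal intubation and need NIV if extubation". Three exclusion criteria in section 10.6 run up to that event or occur at it:

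- criterion 5: "Need for surgery known before the first extubation"
- criterion 6: "Grade IV intraventricular hemorrhage (IVH) occurring before the first extubation"
- criterion 8: "Unplanned extubation"

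After enrolment: section 10.7 lists two withdrawal reasons, the parents' decision and reintubation within the 4-hour crossover. Section 11.5 says withdrawn infants are not replaced. Section 10.14 mentions intention-to-treat only for treatment failure.

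**The concern.** Sealed envelopes protect the allocation until they are drawn. They do nothing about decisions taken between the draw and the first NIV mode. If that interval is more than a few minutes, three things can go wrong.

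1. An infant already randomised can develop a need for surgery, have a grade IV haemorrhage or extubate accidentally. The plan does not say whether that infant is counted.
2. Staff may know the first mode, and with it the second, while choosing when and from what settings to extubate. The pre-extubation settings in section 10.10 are ranges, and the initial NIV settings may be built on them.
3. Calling an extubation planned or unplanned is partly a judgement. Made with the allocation known, it can differ by sequence.

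The outcome most exposed is reintubation within 7 days. Section 7 makes it a parallel comparison of the latter mode, so it rests on the two randomised groups staying intact. The pCO2 contrast is within-infant, and an infant lost before any NIV contributes no pair.

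**Working it through.** **Order of events**

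| Step | Source | Timing stated? |
|---|---|---|
| Infant intubated, no exclusion present, parents approached | 11.4 | Yes |
| Parents sign | 11.4 | Yes, after the approach |
| Envelope drawn | 10.10 | Yes, straight after enrolment |
| Extubation criteria met; routine gas | 10.10 | Before extubation; not placed relative to the envelope |
| First NIV mode | 10.10 | After randomisation; interval not given |

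An infant recruited on the first intubation cannot yet have had an unplanned extubation. On this route criterion 8 can be met only after enrolment, hence after the envelope. Criteria 5 and 6 can be checked at screening, but their windows stay open until extubation.

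**The plan's own sample sizes (section 10.9)**

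Inputs: means 35.1 and 43, SDs 7.5 and 6; proportions 0.10 and 0.17; ratio 1. The selected alpha and beta are not legible. Two-sided 0.05 and 0.2 are the pair that reproduces the results.

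- Continuous: (1.960 + 0.842)² × (7.5² + 6²) / 7.9² = 7.849 × 92.25 / 62.41 = 11.6, so 12 per group.
- Binary: [(1.960 × √(2 × 0.135 × 0.865) + 0.842 × √(0.10 × 0.90 + 0.17 × 0.83)) / 0.07]² = [(0.947 + 0.405) / 0.07]² = 372.9, so 373 per group (401 with continuity correction).

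The plan's figures reproduce, and nothing here changes them. Totals are 24 and 746.

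**Illustration 1: loss unrelated to allocation**

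The documents give no rate, so assume a fraction f of randomised infants is removed and not replaced. Power for 0.10 versus 0.17 with n = 373(1 − f) per group is Φ[(0.07√n − 0.947) / 0.481].

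| f | n per group | Power | Randomised per group to keep 373 |
|---|---|---|---|
| 0 | 373 | 80.0% | 373 |
| 5% | 354 | 78.0% | 393 |
| 10% | 336 | 75.7% | 415 |
| 15% | 317 | 73.3% | 439 |

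In counts, 5% to 15% is 37 to 112 of 746, or 1 to 4 of 24. This is lost precision, with essentially no bias.

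**Illustration 2: loss from one arm only (worst case)**

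Assume the removed infants have a 40% reintubation risk and the arm's full rate is 17%. The observed rate is (0.17 − 0.40f) / (1 − f):

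- f = 5%: 0.150 / 0.95 = 15.8%, a shift of 1.2 points
- f = 10%: 0.130 / 0.90 = 14.4%, a shift of 2.6 points
- f = 15%: 0.110 / 0.85 = 12.9%, a shift of 4.1 points

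If 17% instead describes infants who never meet these criteria, the distortion comes from keeping the others in one arm: 0.17(1 − f) + 0.40f = 18.2%, 19.3% and 20.5%, shifts of 1.2 to 3.5 points. With 13.5% in both arms and a 30% to 50% risk among those removed, removing 5% shifts the arm by 0.9 to 1.9 points and removing 10% by 1.8 to 4.1 points. The planned difference is 17 − 10 = 7 points.

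**The case against.** The strongest reply is that the interval is inferred. Enrolment is never defined relative to extubation. The sequence in section 10.10 (pre-extubation gas, randomisation, NIV) also fits an envelope drawn at the moment of planned extubation, which would leave almost no window. The study flow diagram and a figure in section 10.10 are not reproduced in the available text and may settle this. That stands: the window is possible on the plain reading, not demonstrated.

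A reader might also infer three stronger things that the documents do not support.

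- *That the protocol removes randomised infants who meet these criteria.* It does not say so. Section 10.6 can be read as a screening list (its last item is parental refusal), and section 10.7 does not name these criteria as withdrawals.
- *That this contradicts the intention-to-treat statement.* Section 10.14 confines that statement to treatment failure. Ineligibility before any NIV is not treatment failure, so the text has a gap and not a contradiction.
- *That the oxygen-index stratum is fixed at enrolment.* The time of that measurement is not given.

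The one-sided loss is also a stacked assumption. Surgery and haemorrhage before extubation arise before any study NIV, so the assigned mode cannot cause them, and loss confined to one arm is implausible for them. Only the timing and labelling of extubation are clearly open to influence, and no rate is available for those.

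What the reply does not remove is the written rule itself. It links the envelope to enrolment, enrolment to consent in intubated infants, and neither to extubation.

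**Conclusion.** The point holds as a conditional one. As written, criteria 5, 6 and 8 can be met after open-label randomisation, and the plan is silent on whether such infants are analysed. It goes beyond missing detail, because the stated rule for drawing the envelope is what opens the window and a different rule would close it.

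The threat is mainly to the secondary 7-day reintubation comparison. For pCO2 the consequence is mostly fewer infants. The size cannot be estimated from the documents. Balanced loss of 5% to 15% would cost about 2 to 7 points of power. The 1.2 to 4.1 point shift is a worst case that needs the assumed frequency, the assumed 40% risk and loss from one arm only to hold together; it is not an expected bias. If the site already opens envelopes at planned extubation, the bias is negligible and the change only records practice.

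**What to change.** Keep consent early, and change section 10.10 as follows.

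1. Open the envelope only when the protocol's own extubation criteria are met, the section 10.6 exclusions have been re-checked, and planned extubation is imminent. An infant who meets criterion 5, 6 or 8 before then is recorded as consented but not randomised.
2. Take the oxygen-index stratum from the routine pre-extubation gas.
3. In section 10.14, keep every infant whose envelope was opened in the 7-day reintubation analysis, grouped as randomised, and report any exclusion with its reason by sequence.

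The late envelope makes the third rule workable, since almost every randomised infant would then go straight to the first mode.

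The cost is a few sentences and no change in sample size. The practical burden is that the envelope must be drawn at the bedside at extubation time, including out of hours, so someone other than the dedicated nurse may need access to the envelopes.
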